6.0 DEFINITIONS, COMPUTATIONS, AND CONVENTIONS

6.1 Definitions and Computations

Study Day

Study day will be calculated in reference to the date of first injection (Day 1). For visits conducted on or after the first injection date, study day is calculated as (visit date – first injection date + 1). For visits conducted before the first injection date, study day is calculated as (visit date – first injection date). There will be no Day 0.

Date of First Injection and Date of Last Injection of Study Vaccine

The date of the first injection of study vaccine is defined as the date a subject receives the first injection of the study vaccine. The date of the last injection of study vaccine is the date a subject receives the last injection of the study vaccine.

Treatment-Emergent Period

The reporting period for all non-serious AEs begins at the time of the first study injection (Day 1) through EOS Visit. All AEs will be captured on the AE eCRF.

Any SAE that occurs from the time the consent is signed through EOS Visit, whether or not the SAE is related to the study treatment, must be reported.

The treatment-emergent (TE) period is defined as time from the first study injection through EOS Visit.

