3 STUDY OBJECTIVES AND ENDPOINTS

The study objectives and endpoints are:

Objectives	Endpoints
PART 1	
Primary	

To select one of the two methods of administration of rF1V vaccine with CpG 1018 for Part 2 by comparing humoral immunization response 28 days after the second dose of vaccine	
Ratio of geometric mean ELISA concentration (GMC) between rF1V vaccine with CpG 1018 and rF1V vaccine
Secondary	

To assess the safety and tolerability of rF1V vaccine with CpG 1018 compared with rF1V vaccine	
Rate of reactogenicity: solicited local and systemic post-injection reactionsRate of adverse events (AEs), severe AEs, serious adverse events (SAEs), immune-mediated adverse events of special interest (AESI), and deaths
PART 2	
Primary	

To assess the utility of a 2-dose schedule of rF1V vaccine with CpG 1018 as measured by reduction in time to onset of predicted rF1V protection	
Predicted protection (percentage of subjects reaching the [REDACTED] threshold that corresponds to 50% predicted vaccine efficacy) after 2 doses of rF1V vaccine with CpG 1018 compared to that of 3 doses of rF1V vaccine 
Criterion for evaluation: Similar percentage of subjects reaching the [REDACTED] [REDACTED] threshold that corresponds to 50% predicted vaccine efficacy after 2 doses of rF1V vaccine with CpG 1018 at Day [REDACTED] [REDACTED] compared to that after 3 doses of rF1V vaccine at Day [REDACTED]

To assess the serum [REDACTED] antibody concentration to rF1V with CpG 1018 compared with rF1V vaccine 28 days after the second dose of vaccine	
Ratio of geometric mean ELISA concentration (GMC) between rF1V vaccine with CpG 1018 and rF1V vaccine 28 days after the second dose 
Criterion for evaluation: 2-times increase in [REDACTED] GMC point estimate after the second dose of rF1V vaccine with CpG 1018 to that after the second dose of rF1V vaccine at Day [REDACTED]

Secondary	

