6.2.2 Study Vaccine Administration

Designated unblinded study-site personnel will be responsible for preparing and administering the study injection. These individuals will not be blinded to the treatment assignment in order to prepare and administer the study injections, which will be prepared at a location isolated from blinded personnel. These individuals will not be involved in assessing safety and laboratory data and will be instructed not to communicate treatment assignments to blinded study personnel.

The unblinded study personnel should ensure that a physical barrier is used to obstruct the view of the investigational product and that the subject turns their head away from the arm being injected to prevent the subject becoming aware of their treatment assignment.

6.2.2.1 Part 1

Group 1: 0.5 mL of rF1V vaccine and 0.25 mL of CpG 1018 will be administered intramuscularly in the same or nearby location of the deltoid muscle of the non-dominant arm on Days [REDACTED].

Group 2: 0.75 mL of the bedside mix of rF1V vaccine and CpG 1018 and 0.25 mL of placebo will be administered intramuscularly in the same or nearby location of the deltoid muscle of the non-dominant arm on Days [REDACTED]
[REDACTED]

Group 3: 0.5 mL of rF1V vaccine and 0.25 mL of placebo will be administered intramuscularly in the same or nearby location of the deltoid muscle of the non-dominant arm on Days [REDACTED]
[REDACTED]

6.2.2.2 Part 2

Scenario 1: Group 1 is selected.

Group 1: 0.5 mL of rF1V vaccine and 0.25 mL of CpG 1018 will be administered intramuscularly in the same or nearby location of the deltoid muscle of the non-dominant arm on Days [REDACTED]

Group 3: 0.5 mL of rF1V vaccine and 0.25 mL of placebo will be administered intramuscularly in the same or nearby location of the deltoid muscle of the non-dominant arm on Days [REDACTED]
[REDACTED]

Scenario 2: Group 2 is selected.

Group 2: 0.75 mL of the bedside mix of rF1V vaccine and CpG 1018 will be administered intramuscularly in the deltoid muscle of the non-dominant arm on Days [REDACTED] and 0.25 mL placebo will be administered on Day [REDACTED]

Group 3: 0.5 mL of rF1V vaccine will be administered intramuscularly in the same or nearby location of the deltoid muscle of the non-dominant arm on Days [REDACTED]

Study treatments are presented in [Table 7-1](#).

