9.4.1 Vital Signs

Vital signs will include oral temperature and measurements of heart rate, respiratory rate, systolic and diastolic blood pressure. Vital signs taken at the Day 1, Day 29, and Day 183 visits will be measured prior to study vaccine administration.

Vital signs will be recorded as indicated in the Schedule of Events ([Appendix 1](#)).

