2.0 STUDY OVERVIEW

This is a phase 2, randomized, active-controlled, observer-blinded, multicenter trial of the immunogenicity, safety, and tolerability of rF1V vaccine with CpG 1018 compared with rF1V vaccine alone in adults. Approximately two hundred healthy adults 18 to 55 years of age will be enrolled to compare a two-dose regimen of rF1V with CpG 1018 administered on study Days [REDACTED] with a three-dose regimen of rF1V vaccine alone administered on [REDACTED].

The study will be conducted in 2 parts (Part 1 and Part 2). The table below outlines study drug administration in both parts. When investigational product is co-administered as 2 separate injections, the injections should be administered in close physical proximity to each other (within approximately 1 inch).

Injections will be administered by study personnel not otherwise involved in the subjects' safety evaluation. Recording and evaluation of safety information and laboratory data will be performed by observers blinded to the subjects' treatment assignment.

Part 1:

There will be 2 methods of rF1V vaccine with CpG 1018 administration:

- Group 1 (N = approximately 20): rF1V vaccine and CpG 1018 will be co-administered as 2 separate injections on Days 1 [REDACTED]
[REDACTED].
- Group 2 (N = approximately 20): bedside mix of rF1V vaccine + CpG 1018 (administered as 1 injection) and placebo will be administered as 2 separate injections on [REDACTED]

In addition, rFIV vaccine will be administered alone without CpG 1018:

- Group 3 (N=20): rF1V vaccine and placebo will be administered as 2 separate injections on Days [REDACTED]

All Groups will receive 2 injections at each treatment visit to maintain the blind.

Part 2: Part 2 will begin after immunogenicity assessments from the [REDACTED] visit in Part 1 are completed. The method of vaccine administration method that is selected from Part 1 will be evaluated in Part 2.

- Group 1 (if selected) (N=70): rF1V vaccine co-administered with CpG 1018
- Group 3 (N=70): rF1V vaccine co-administered with placebo

OR

- Group 2 (if selected) (N = 70): bedside mix of rF1V vaccine and CpG 1018
- Group 3 (N=70): rF1V vaccine

Subjects will be followed through Day 393 (Week 56)

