5.3 Immunogenicity Population

The modified intent-to-treat (mITT) population will comprise all eligible subjects who received at least 1 dose of study vaccine and have a post-injection immunogenicity evaluation.

The per-protocol (PP) population for the immunogenicity analyses will comprise Groups 1 and 2 subjects who received 2 doses of study vaccine and Group 3 subjects who received 3 doses of study vaccine, have no major protocol deviations (see Section 8.2), and have immunogenicity data obtained within the study visit window at Day █ for Groups 1 and 2 and Day █ for Group 3.

Note: the PP population definition and major protocol deviations in Section 8.2 are updated from the Protocol Amendment 5.

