8.7 Safety Analyses

Vaccine exposure and compliance will be summarized descriptively for safety population.

Safety data will be analyzed descriptively and will be based on the safety population. The safety parameters will be presented for all sites combined. Summary statistics will be used to describe the incidence of all post-injection reactions (PIRs) and AEs, including SAEs, deaths, acute myocardial infarctions (AMIs), and AESIs. AMIs include the events with PTs of Acute Myocardial Infarction, Acute Coronary Syndrome, or Myocardial Infarction. The incidence and proportion of post-injection reactions and AEs will be summarized. AEs will be coded using the MedDRA SOC and PT.

The treatment-emergent period is defined in [Section 6.1](#).

On Day █ Day █, and Day █, subjects will be asked to complete an e-diary (or equivalent) to record any solicited local and systemic reactions during the 7-day follow-up period after vaccination. Post-injection reactions persisting beyond 7 days after injection are considered to be AEs and need to be recorded and reported as AEs (see protocol Section 10.2). The severity of the post-injection reactions will be graded using the United States Food and Drug Administration's (FDA) Guidance for Industry: Center for Biologics Evaluation and Research (CBER) Toxicity Grading Scale for Healthy Adult and Adolescent Volunteers Enrolled in Preventive Vaccine Clinical Trials.

Local reactions include pain, redness, pruritus and swelling, and systemic reactions include fatigue, temperature, chills, malaise, myalgia, vomiting, diarrhea, and headache.

Post-injection reactions reported from day 1 to day 7 will be summarized by maximal severity and by vaccine group. The severity of local reactions, including redness and swelling will be categorized as none (:S25mm), >25 to :S50mm (mild), >50 to :S100mm (moderate) and >100mm (severe).

The severity of local reactions including pain, and pruritus and systemic reactions including fatigue, chills, malaise, myalgia, vomiting, diarrhea and headache occurring up to 7 days after each vaccination will be categorized as none, mild (no interference with activity), moderate (some interference with activity), severe (significant, prevents daily activity).

Temperature will be categorized as <38°C (no fever), 38-38.4°C (mild), 38.5-38.9°C (moderate), 39-40°C (severe) and >40°C (life threatening).

Each local and systemic reaction will also be categorized as none vs. any.

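### The adverse event tables listed in SAP 8.7 compare two active doses with three over the whole study, and none isolates the period of equal active exposure

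*SAP*

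**What the plan says.** The safety objective, secondary in both parts, is "To assess the safety and tolerability of rF1V vaccine with CpG 1018 compared with rF1V vaccine" (Protocol 3, repeated in SAP 3.0). Its endpoint rates carry no time window.

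The arms differ in active doses. The per-protocol definition in SAP 5.3 refers to "Groups 1 and 2 subjects who received 2 doses of study vaccine" and "Group 3 subjects who received 3 doses of study vaccine". Three injection visits can be read from Protocol 9.4.1: "Vital signs taken at the Day 1, Day 29, and Day 183 visits will be measured prior to study vaccine administration". Protocol 7.5.1 also ties the third injection to Day 183. For Group 2 in Part 2, Protocol 6.2.2.2 says that "0.25 mL placebo will be administered on Day" followed by a redacted day; placebo is normal saline (Protocol 6.1.3). The matching text for Group 1, and Table 7-1, are redacted.

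For AEs, SAP 6.1 states: "The treatment-emergent (TE) period is defined as time from the first study injection through EOS Visit". Under SAP 8.7 a subject with repeated events is counted once, at worst severity and strongest relationship. The ten AE summaries listed there cover TEAEs, Grade 3 or above, related events, SAEs, deaths, discontinuations, AMI and AESIs. None is described as by dose or by interval. SAP 8.8 plans no other analyses.

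Reactions are treated differently. Diaries cover seven days after each vaccination, and "Post-injection reactions reported from day 1 to day 7 will be summarized by maximal severity and by vaccine group". SAP 8.7 also plans tables of any local or systemic reaction both overall and by time point.

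**The concern.** The objective asks how rF1V with CpG compares with rF1V alone. Up to the third injection the groups have the same number of active doses on the same days, so a difference in AE rates can be attributed to CpG, chance aside. At Day 183 only the control receives active vaccine again. Days 183 to 393 make up 211 of the 393 days, or 54% of the treatment-emergent period.

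A subject-level rate over the whole period therefore mixes two effects: any CpG excess at doses 1 and 2, which raises the CpG rate, and the third active dose, which raises the control rate. Similar whole-period rates could mean that CpG adds nothing, or that the two effects cancel. Protocol 2.4.2 says that no clinical data exist for CpG 1018 added to rF1V, so these tables will be the first evidence on the question.

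**Working it through.** The plan has no safety figure to reproduce. Its only design calculation (SAP Table 4-1) concerns immunogenicity, and neither document states a reaction or AE rate expected in this trial. All rates below are assumptions.

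**1. Any reaction, visits independent.** Let c be the per-dose rate with rF1V alone, t with CpG and s with saline.

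- Whole study: control 1 − (1 − c)³; CpG 1 − (1 − t)²(1 − s).
- Two common doses: control 1 − (1 − c)²; CpG 1 − (1 − t)².

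| c, t, s | Whole study, CpG v control | Two common doses, CpG v control |
|---|---|---|
| 40%, 50%, 20% | 80.0% v 78.4% (+1.6 points) | 75.0% v 64.0% (+11.0) |
| 40%, 50%, 10% | 77.5% v 78.4% (−0.9) | 75.0% v 64.0% (+11.0) |
| 40%, 40%, 20% (no CpG effect) | 71.2% v 78.4% (−7.2) | 64.0% v 64.0% (0) |

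First row: 1 − 0.5² × 0.8 = 0.800 and 1 − 0.6³ = 0.784; then 1 − 0.5² = 0.750 and 1 − 0.6² = 0.640.

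**2. Correlation within subjects.** The same rates with a shared normal frailty, for the 40%, 50%, 20% case and then the no-effect case:

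| Latent correlation | Whole study | Two doses | No effect, whole study |
|---|---|---|---|
| 0 | +1.6 | +11.0 | −7.2 |
| 0.5 | +3.4 | +10.6 | −6.0 |
| 0.8 | +5.3 | +10.3 | −4.5 |

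Masking shrinks but remains. It disappears only if the same subjects react at every active dose.

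**3. Adverse events, where the gap lies.** Assume a background risk b over 393 days, spread evenly, plus an independent risk per active dose and none from saline. Take b = 40%, c = 10% and t = 15%, a 1.5-fold excess.

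- Whole period: control 1 − 0.6 × 0.9³ = 56.3%; CpG 1 − 0.6 × 0.85² = 56.7%. Difference +0.4 points.
- Days 1 to 182: the chance of no background event is 0.6^(182/393) = 0.789. Control 1 − 0.789 × 0.9² = 36.1%; CpG 1 − 0.789 × 0.85² = 43.0%. Difference +6.9 points.

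Ranges over b = 20% to 60% and c = 5% to 20%:

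| Per-dose excess | Whole period | Days 1 to 182 |
|---|---|---|
| 1.5-fold | +0.1 to +1.8 points | +3.1 to +13.5 points |
| 1.25-fold | −0.9 to −4.0 points | +1.5 to +7.0 points |

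**4. Precision.** With 90 per arm, the 95% half-width for 43.0% v 36.1% is 1.96 × √[(0.430 × 0.570 + 0.361 × 0.639)/90] = 14 points. The cut removes a systematic offset; it does not make the comparison precise.

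**The case against.** The strongest reply is that the plan does what the design declares. Protocol 4.1 sets a two-dose regimen against a three-dose regimen, and the whole-period rates answer the safety question for those regimens. The safety objective names no per-dose estimand, and the definition in SAP 6.1 is an ordinary one. This stands: the tables are not wrong and should stay. Follow-up to Day 393 also matters in its own right, since Protocol 10.8 has AESIs assessed throughout the trial.

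A reader might infer that the plan as a whole hides reactogenicity due to CpG. The documents do not support that. With seven-day diaries and tables by time point, an excess after dose 1 or dose 2 would be visible like for like. Only the overall reaction rate, read alone, is affected. What remains is that time point is not expressly defined as dose number.

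A reader might also take a placebo-only third visit as documented for every CpG group. It is readable only for Group 2 in Part 2. For Group 1, and for Part 1, it is inferred from the two-dose definition and the rule that all Part 1 groups receive two injections at each visit.

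Two further points stand in part. Table lists and specifications are in separate documents (SAP 8.0 and 11.0), so the absence of a cut can be asserted only for the SAP text. Listings of all TEAEs would allow a later split, but one chosen after unblinding carries less weight than one written down beforehand. That safety is descriptive does not remove the issue, because descriptive tables still carry the safety conclusion.

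**Conclusion.** The point holds for the AE tables and is a cheap improvement rather than a fault in the regimen comparison. As listed, those tables compare two active doses with three, and none compares the arms at equal active exposure. Under the assumed AE rates, a 1.5-fold per-dose excess almost vanishes over the whole period and a 1.25-fold excess changes sign, while both keep the right direction before the third injection. For reactions the matter is confined to the overall rate.

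The size rests on assumed rates, independence between visits, an even background AE rate and no AE risk from saline. Correlation within subjects would reduce the reaction masking. The direction of the offset needs only that a third active dose causes more events than the saline given in its place.

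**What to change.** In SAP 8.7:

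1. Keep the AE tables from first injection to EOS and label them as regimen-level, two active doses v three.
2. Add the same tables (TEAEs, Grade 3 or above, related AEs, SAEs, AESIs) restricted to events starting from the first injection until before the third injection at Day 183. Name these as the pre-specified like-for-like comparison of rF1V with CpG against rF1V alone.
3. State that time point in the reaction tables means dose number, and give the overall reaction rate the same regimen-level label.

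The cost is one date cut on tables already planned, some SAP wording and a second set of descriptive AE columns. Dosing, visits and data collection do not change.

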6.2 Conventions

Unless otherwise specified, the following conventions will be applied to all analyses:

- Age will be calculated by the following SAS code:

If only year of birth is given, then Age = (Year of Screening – Year of Birth). Otherwise
age = floor ((intck('month', birth_date, consent_date) -
(day(consent_date) < day(birth_date))) / 12);

- 1 pound = 0.454 kg
- 1 inch = 2.54 cm
- Temperature will be converted from Fahrenheit to Celsius using the following formula: (temperature°F - 32) x 5/9
- Missing safety data will not be imputed unless otherwise specified.
- For immunogenicity results, the [REDACTED] concentrations are obtained using the ELISA assay. For concentration reported as <value, half of the value will be used in calculation. For concentration reported as >value, value+1 will be used in calculation.
- For unsolicited safety analyses, percentages will be calculated based on the number of subjects in the analysis population.
- For by-visit observed data analyses, percentages will be calculated based on the number of subjects with nonmissing data as the denominator unless otherwise specified.
- For other continuous endpoints, the summary statistics will include mean, standard deviation, median, and range (minimum and maximum).
- For categorical endpoints, the summary statistics will include counts and percentages.

- AEs and medical history will be coded using the Medical Dictionary for Regulatory Activities (MedDRA) Version 23.1 or higher.
- Prior therapies and concomitant medications will be coded using the World Health Organization (WHO) Drug Dictionary Version 202009 or higher.

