9.4.3 Laboratory Assessments

Laboratory assessments are listed below and will be performed according to the Schedule of Events (Appendix 1). Sample collections will be prior to administration of the study vaccine on injection days.

- HIV, HBV, HCV testing at Screening Visit
- Pregnancy testing: For female of childbearing potential (ie, onset of menarche), a serum pregnancy test will be performed at screening and must be negative for the subject to participate. Additionally, a urine pregnancy test will be performed within 24 hours prior to administration of each study vaccine and must be negative for the subject to receive study injection.
- Chemistry Panel: sodium, potassium, chloride, bicarbonate, blood urea nitrogen (BUN), creatinine, glucose, calcium, aspartate transaminase (AST), alanine transaminase (ALT), lactate dehydrogenase (LDH), bilirubin, alkaline phosphatase
- Hematology: red blood cell count, hemoglobin, hematocrit, white blood cell count with differential, and platelet count
- Reserve serum aliquot specimens will be collected and stored frozen at a central location for possible future testing

Additional details for collection and processing of laboratory samples are provided in the Laboratory Manual.

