8.0 STATISTICAL METHODS

This is a phase 2, randomized, active-controlled, observer-blinded, multicenter trial of the immunogenicity, safety, and tolerability of rF1V vaccine with CpG 1018 compared with rF1V vaccine alone in adults.

Part 1 objectives will be evaluated descriptively. The administration method of vaccine utilized in Part 2 of the study will be selected by Dynavax in consultation with the Department of Defense (DoD) after Day 57 immunogenicity data become available to determine whether the GMC 1 month after 2 doses of rF1V vaccine with CpG 1018 using the selected administration method is at least 2 times higher than that 4 weeks after 2 doses of rF1V vaccine in Group 3.

The proposed statistical planning for Part 2 is presented according to the objectives. Data from Part 1 and Part 2 will be combined to evaluate the Part 2 objectives. No multiplicity adjustments are made, and all statistical tests will be conducted at 5% two-sided Type I level unless otherwise specified. All confidence intervals are two-sided 95% confidence intervals unless otherwise specified.

All analyses of demographics and baseline characteristics, medical history, vaccine exposure and safety will be summarized in a descriptive manner. In general, continuous variables will

be summarized by number of subjects, mean, standard deviation, median, quartiles, minimum and maximum, and categorical variables will be summarized by number and percentage of subjects in each study group as appropriate. All data processing, summarization, and analyses will be performed using SAS Version 9.4 or higher. Specifications for tables, graphs, and data listings will be provided in the tables, figures, listings (TFL) specifications document as needed. No specific safety hypotheses will be tested.

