8.6 Immunogenicity Analyses

The primary and other immunogenicity endpoints will be analyzed using the mITT population. Sensitivity analyses on immunogenicity data will also be presented using the PP population.

Immunogenicity will be measured by serum rF1V [REDACTED] concentration at each visit.

Data from Part 1 subjects and Part 2 subjects will be combined to evaluate the Part 2 objectives. No multiplicity adjustment is proposed.

Additional analyses may be attempted, including analysis to quantify antibody decay over time.

Part 1 Primary Objective: To select one of the two methods of administration of rF1V vaccine with CpG 1018 for Part 2 by comparing humoral immunization response 28 days after the second dose of vaccine

Endpoint: Ratio of geometric mean ELISA concentrations (GMCs) between rF1V vaccine with CpG 1018 and rF1V vaccine.

Estimand: GMCs and associated two-sided 95% confidence intervals for each of the 3 study groups will be computed by exponentiating the mean and associated Student's t confidence interval of the log10 transformed individual antibody concentrations assuming Normal distribution. The ratio of GMCs and associated two-sided 95% confidence interval will be compared between rF1V vaccine with CpG 1018 and rF1V vaccine, using Student's t method. The ratio of GMCs and associated two-sided 95% confidence interval between two administration methods of rF1V vaccine with CpG 1018 vaccines will also be produced.

Criterion for evaluation: GMC 1 month after 2 doses of rF1V vaccine with CpG 1018 using the selected administration method is at least 2 times higher than that 4 weeks after 2 doses of rF1V vaccine.

Part 2 Primary Objective 1: To assess the utility of a 2-dose schedule of rF1V vaccine with CpG 1018 as measured by reduction in time to onset of predicted rF1V protection

Endpoint: Predicted protection (percentage of subjects reaching the [REDACTED] threshold that corresponds to 50% predicted vaccine efficacy) at Week [REDACTED] after 2 doses of rF1V vaccine with CpG 1018 as that at Week [REDACTED] after 3 doses of rF1V vaccine without CpG 1018. The [REDACTED] threshold that corresponds to 50% predicted vaccine efficacy will be obtained from a model using [REDACTED] data after 3 doses of rF1V vaccine (or after 2 doses of rF1V

with CpG 1018 TBD) in this study. The threshold and the model used will be described in a separate report. Part 2 Primary Objective 1 can only be evaluated after the determination of this threshold.

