Estimand: Percentage of subjects reaching the [REDACTED] threshold and associated 95% two-sided Clopper-Pearson confidence intervals will be computed. Fisher's exact tests will be used to compare predicted protection rate between study groups.

Criterion for evaluation: Similar percentage of subjects reaching the [REDACTED] threshold that corresponds to 50% predicted vaccine efficacy after 2 doses of rF1V vaccine with CpG 1018 as compared to that after 3 doses of rF1V vaccine.

Part 2 Primary Objective 2: To assess the serum [REDACTED] concentration to rF1V vaccine with CpG 1018 compared with rF1V vaccine 28 days after the second dose of vaccine

Endpoint: Ratio of geometric mean ELISA concentration (GMC) between rF1V vaccine with CpG 1018 and rF1V vaccine at Week [REDACTED].

Estimand: GMCs and associated two-sided 95% confidence intervals will be computed by exponentiating the mean and associated Student's t confidence interval of the log10 transformed individual antibody concentrations assuming Normal distribution. The ratio of GMCs and associated two-sided 95% confidence interval will be compared between rF1V vaccine with CpG 1018 and rF1V vaccine, using ANOVA if site can be used as an adjustment factor in the model or Student's t method.

Criterion for evaluation: 2-times increase in [REDACTED] GMC point estimate after the second dose of rF1V vaccine with CpG 1018 to that after the second dose of rF1V vaccine.

Part 2 Secondary Objective: To assess the serum [REDACTED] concentration to rF1V with CpG 1018 at selected time points after each dose

Endpoint: GMC and seroconversion rate of serum rF1V [REDACTED] titers at the following selected time points after each dose of vaccine:

- [REDACTED]

- [REDACTED]

[figure not shown]
Seroconversion is defined as the presence of detectable antibody in subjects who had no detectable antibody levels at Day 1, or a 2: 2-fold increase in antibody level in subjects who had detectable antibody levels at Day 1.

Estimand: GMCs and associated two-sided 95% confidence intervals will be computed by exponentiating the mean and associated Student's t confidence interval of the log10 transformed individual antibody concentrations assuming Normal distribution.

Seroconversion rate and associated 95% two-sided Clopper-Pearson confidence intervals will be computed.

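### Entering above-range ELISA results as value+1 can attenuate the GMC ratio that is read against 2, and the SAP has no censored-data analysis to show by how much

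*SAP*

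**What the plan says.** SAP 6.2 (Conventions) sets two substitution rules for the ELISA. At the top of the range: "For concentration reported as >value, value+1 will be used in calculation". At the bottom, half of the reporting limit is entered instead.

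SAP 8.6 obtains each GMC by "exponentiating the mean and associated Student's t confidence interval of the log10 transformed individual antibody concentrations assuming Normal distribution". The ratio and its interval come from Student's t or, for Part 2 primary objective 2, from ANOVA if site can be included. Substituted values enter as ordinary observations.

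Two criteria compare that ratio with 2:
- **Part 1 selection:** the GMC "using the selected administration method is at least 2 times higher than that 4 weeks after 2 doses of rF1V vaccine".
- **Second primary objective of Part 2:** a "2-times increase in [REDACTED] GMC point estimate after the second dose of rF1V vaccine with CpG 1018", with the control arm at the same point as comparator. No confidence bound is required.

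The per-protocol sensitivity analysis in SAP 8.6 changes the subjects, not the substitution rule. No censored-data analysis and no tabulation of out-of-range results is described, and SAP 8.8 plans no other analyses. The documents do not give the upper limit of the assay or say whether high samples are diluted and re-run. Protocol 9.4.3 refers laboratory detail to a Laboratory Manual. It also states: "Reserve serum aliquot specimens will be collected and stored frozen at a central location for possible future testing".

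**The concern.** A result reported as above the limit is right-censored: the true concentration is at least the limit and may be far higher. Value+1 is in effect the limit itself. The added 1 raises a limit of 1000 by 0.1%.

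The trial looks for at least a doubling with CpG. With similar spread in both arms, more CpG than control samples would then lie above any fixed limit at the same visit. The cap removes more from the CpG mean, and the ratio moves towards 1. Because the Part 2 criterion is a bare point estimate, a modest shift can change the reading when the true ratio is not far above 2. The same ratio informs the choice of administration method in Part 1, where there are about 20 subjects per group.

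**Working it through.** **The plan's own figure.** The only sample-size figure is SAP Table 4-1 (Protocol Table 11-1). It reproduces with exact Clopper-Pearson limits: 81/85 gives 88.4–98.7%, 79/85 gives 85.3–97.4% and 77/85 gives 82.3–95.9%. It concerns primary objective 1. No SD, power or expected ratio is stated for the GMC ratio, so there is no figure to reproduce for this endpoint.

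**Inputs.** From the documents: the value+1 rule, the mean of log10 values, the criterion of 2, 85 evaluable per arm, and about 20 per group in Part 1. Assumed: Normal log10 titres (as SAP 8.6 assumes), SD s equal in both arms and between 0.4 and 0.6, the true ratio R, and the share p of control samples above range.

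**Formula.** Set the control log10 mean to 0 and the CpG mean to μ = log10 R. The limit is c = s·z(1−p). With k = (c−μ)/s, the expected capped value in an arm is

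E[min(X,c)] = μΦ(k) − sφ(k) + c[1−Φ(k)],

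and the observed ratio is 10 to the power of the difference between arms.

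**Worked case: R = 2, s = 0.5, p = 5%.** The limit is c = 0.5 × 1.645 = 0.822.
- Control: −0.5 × 0.1031 + 0.822 × 0.05 = −0.0104.
- CpG: μ = 0.3010, k = 1.043, Φ = 0.8515, φ = 0.2316. So 0.3010 × 0.8515 − 0.5 × 0.2316 + 0.822 × 0.1485 = 0.2627. About 15% of CpG samples are above range.
- Ratio: 10^(0.2627 + 0.0104) = 10^0.2731 = 1.875.

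**Across s = 0.4 to 0.6:**

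| Control above range | CpG above range (true 2.0) | True 2.0 reads | True 2.5 reads |
|---|---|---|---|
| 1% | 3–6% | 1.96–1.97 | 2.41–2.44 |
| 5% | 13–19% | 1.86–1.89 | 2.21–2.28 |
| 10% | 22–30% | 1.76–1.80 | 2.03–2.13 |

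**Chance that the point estimate reaches 2** (20,000 simulated trials per setting):
- 85 per arm, true 2.0, 5% of control above range: 28–39%, against 50% without the cap.
- 85 per arm, true 2.2, 5%: 51–55%, against 67–75%.
- 85 per arm, true 2.5, 10%: about 55–64%, against 85–94%.
- 20 per arm (Part 1), true 2.5, 10%: 53–57%, against 70–78%.

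**How much censoring brings the expected ratio down to 2** (s = 0.3 to 0.6, share of CpG samples above range): 6–8% at a true 2.05, 22–30% at 2.25, 35–47% at 2.5 and 52–67% at 3.

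**Unequal spread.** With control SD 0.6, CpG SD 0.3 and 5% of control above range, a true 2.0 reads 2.05 and a true 2.5 reads 2.56. With SDs of 0.5 and 0.4, in either order, a true 2.0 still reads low (1.97 or 1.74).

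**Does a censored fit recover the ratio?** In 300 simulated trials per setting (85 per arm, SD 0.5, 20% of CpG above range), a true 2.5 reads 2.26 under value+1 and 2.51 under a right-censored Normal likelihood. A true 2.25 reads 2.03 and 2.25.

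**The case against.** The strongest reply is that the rule is a conditional convention. Nothing in the documents says that any sample after the second dose will be reported above range, and the Laboratory Manual, which is not among the documents, may require dilution into range. If so, the effect is zero. This stands: every SD, true ratio and above-range share used here is an assumption.

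A reader might infer that the rule pulls the ratio below 2. The documents do not support that. Even with 10% of control samples above range, a true 2.5 still reads 2.03–2.13. An expected ratio below 2 needs a true ratio close to 2 or a large share of CpG samples above range. A reader might also infer that the CpG arm is always cut more. That needs roughly similar SDs, and the unequal-spread case shows the direction can reverse.

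At a true ratio of exactly 2.0, the point-estimate criterion is missed about half the time with no cap at all, so only the extra loss belongs to this rule. Part 1 is evaluated descriptively, and the sponsor chooses the method in consultation with the Department of Defense. It is not a mechanical pass/fail test.

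Two further extensions should not be drawn. The cap may narrow the t interval, but no confidence bound enters the Part 2 criterion. The half-value rule has no predictable direction and applies where titres are low, whereas both criteria are read after the second dose.

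Finally, the substitution rule usually errs against the CpG arm, and Part 1 data are reviewed unblinded and then pooled into Part 2. That is a fair reason not to insist on replacing the primary estimator.

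**Conclusion.** The concern holds as a conditional one. If results are above range and the arms have similar spread, value+1 attenuates the GMC ratio used for Part 1 selection and Part 2 primary objective 2, and nothing planned would reveal it. Under equal log10 SDs of 0.4 to 0.6, the loss at a true 2.0 is about 2% when 1% of control samples are above range, 6–7% at 5% and 10–12% at 10%. It matters most when the true ratio is a little above 2, where the chance of meeting the criterion can drop by 12 to 24 percentage points (true 2.2, 5% of control above range).

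The actual size is unknown because the documents do not give the upper limit, the dilution practice, the SD or the expected ratio. The usual consequence is a false miss or an understated effect.

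**What to change.** In SAP 6.2 and 8.6:
- State the upper limit and how above-range samples are handled. Where dilution and re-assay give a measured result, use it. Reserve serum may make this possible.
- For the remaining out-of-range results, pre-specify a censored lognormal analysis of the GMC ratios (for example SAS PROC LIFEREG), with `>value` right-censored, `<value` left-censored, and group and, where used, site in the model. Report it beside the substitution analysis, at minimum as a named sensitivity analysis.
- Tabulate the number of `>value` and `<value` results by arm and visit.

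The cost is SAP wording and one standard procedure. Its drawback is reliance on the Normal log10 assumption, which the SAP already makes. If no result is out of range, the GMC ratio does not change.
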